9.1 Independent Ethics Committee or Institutional Review Board

Country regulations, US federal regulations, and the ICH guidelines require that approval be obtained from an IRB or IEC before participation of human participants in research studies. Before study onset, the protocol, ICF, advertisements to be used for the recruitment of study participants, and any other written information regarding this study to be provided to the participant or the participant's legal guardian must be approved by the IRB/IEC.

Documentation of all IRB/IEC approvals and of the IRB/IEC compliance with ICH harmonised tripartite guideline E6(R2): GCP and with applicable regulations in the countries where the study will be conducted will be maintained by the site and will be available for review by the sponsor or its designee.

All IRB/IEC approvals must be signed by the IRB/IEC chairman or designee and must identify the IRB/IEC name and address, the clinical protocol by title or protocol number or both, and the date approval or a favorable opinion was granted.

The investigator is responsible for providing written summaries of the progress and status of the study at intervals not exceeding 1 year or otherwise specified by the IRB/IEC. The investigator must promptly supply the sponsor or its designee, the IRB/IEC, and, where applicable, the institution, with written reports on any changes significantly affecting the conduct of the study or increasing the risk to participants.

9.2 Ethical Conduct of the Study

The study will be performed in accordance with the ethical principles that have their origin in the Declaration of Helsinki, ICH GCP, and all applicable country and local regulations.

9.3 Participant Information and Consent

A written informed consent in compliance with regulatory authority regulations or US Title 21 CFR Part 50 shall be obtained from each participant before entering the study or performing any unusual or nonroutine procedure that involves risk to the participant. An informed consent template may be provided by the sponsor to investigative sites. If any institution-specific modifications to study-related procedures are proposed or made by the site, the consent should be reviewed by the sponsor or its designee or both before IRB/IEC

submission. Once reviewed, the consent will be submitted by the investigator to his or her IRB/IEC for review and approval before the start of the study. If the ICF is revised during the study, all active participants must be reconsented by signing the revised form.

Before recruitment and enrollment, each prospective participant or his or her legal guardian will be given a full explanation of the study, be allowed to read the approved ICF, and have any questions answered. Once the investigator is assured that the participant/legal guardian understands the implications of participating in the study, the participant/legal guardian will be asked to give consent to participate in the study by signing the ICF. The authorized person obtaining the informed consent also signs the ICF.

The ICF will contain a separate section that addresses the use of remaining mandatory samples for optional exploratory research (if applicable) and explain/address the exploratory research portion of the study. Participant medical records need to state that written informed consent was obtained.

The investigator shall retain the signed original ICF(s) and give a copy of the signed original form to the participant or legal guardian.

10 Investigator's Obligations

The following administrative items are meant to guide the investigator in the conduct of the study but may be subject to change based on industry and government standard operating procedures, working practice documents, or guidelines. Changes will be reported to the IRB/IEC but will not result in protocol amendments.

10.1 Confidentiality

All laboratory specimens, evaluation forms, reports, and other records will be identified in a manner designed to maintain participant confidentiality. All records will be kept in a secure storage area with limited access. Clinical information will not be released without the written permission of the participant (or the participant's legal guardian), except as necessary for monitoring and auditing by the sponsor, its designee, the FDA, or the IRB/IEC.

The investigator and all employees and coworkers involved with this study may not disclose or use for any purpose other than performance of the study any data, record, or other unpublished, confidential information disclosed to those individuals for the purpose of the study. Prior written agreement from the sponsor or its designee must be obtained for the disclosure of any said confidential information to other parties.

10.2 Financial Disclosure and Obligations

Investigators are required to provide financial disclosure information to allow the sponsor to submit the complete and accurate certification or disclosure statements required under 21 CFR 54. In addition, the investigator must provide to the sponsor a commitment to promptly update this information if any relevant changes occur during the investigation and for 1 year following the completion of the study.

Neither the sponsor nor [REDACTED] is financially responsible for further testing or treatment of any medical condition that may be detected during the screening process. In addition, in the absence of specific arrangements, neither the sponsor nor [REDACTED] is financially responsible for further treatment of the participant's disease.

10.3 Investigator Documentation

Prior to beginning the study, the investigator will be asked to comply with ICH E6(R2) Section 8.2 and Title 21 of the CFR by providing all essential documents.

10.4 Study Conduct

The investigator agrees that the study will be conducted according to the principles of ICH E6(R2). The investigator will conduct all aspects of this study in accordance with all national, state, and local laws or regulations. Study information from this protocol will be posted on publicly available clinical trial registers before enrollment of participants begins.

The investigator agrees to conduct the study as outlined in this protocol in accordance with ICH E6(R2) and all applicable guidelines and regulations.

10.5 Adverse Events and Study Report Requirements

The investigator agrees to submit reports of SAEs to the sponsor and/or IRB/IEC according to the timeline and method outlined in the protocol (Section 6.2.1.3.1). In addition, the investigator agrees to submit annual reports to the study site IRB/IEC as appropriate.

10.6 Investigator's Final Report

Upon completion of the study, the investigator, where applicable, should inform the institution. Also, the investigator/institution should provide the IRB/IEC with a summary of the study's outcome and provide the sponsor and regulatory authority(ies) with any reports required.

10.7 Records Retention

Essential documents should be retained until at least 2 years after the last approval of a marketing application in an ICH region and until there are no pending or contemplated marketing applications in an ICH region or at least 2 years have elapsed since the formal discontinuation of clinical development of the study drug. These documents should be retained for a longer period, however, if required by the applicable regulatory requirements or by an agreement with the sponsor. It is the responsibility of the sponsor to inform the investigator/institution as to when these documents no longer need to be retained. No records may be transferred to another location or party without written notification to the sponsor.

11.1 Monitoring

11.1.1 Safety Review Committee

There will be no safety review committee or data monitoring committee.

11.1.2 Monitoring of the Study

This study will be monitored according to an approved monitoring plan based on the objectives, purpose, design, and complexity of the study. The investigator will allocate adequate time for all monitoring visits and between visits to facilitate the requirements of the study and study timelines. The investigator will also ensure that the monitor or other compliance or quality assurance reviewer is given direct access to all study-related documents and study-related facilities (eg, pharmacy, diagnostic laboratory), phone, fax, and internet and has adequate space to conduct the monitoring visit. Site monitoring is conducted to ensure that the rights of human participants are protected, that the study is implemented in accordance with the protocol and/or other operating procedures, and that the study uses high quality data collection processes. The monitor will evaluate study processes based on Evelo or designee standards, ICH E6, and all applicable, regulatory guidelines.

11.1.3 Inspection of Records

Investigators and institutions involved in the study will permit study-related monitoring, audits, IRB/IEC review, and regulatory inspections by providing direct access to all study records. In the event of an audit, the investigator agrees to allow the sponsor, representatives of the sponsor, or a regulatory agency (eg, FDA or other regulatory agency) access to all study records.

The investigator should promptly notify the sponsor and [REDACTED] of any audits scheduled by any regulatory authorities and promptly forward copies of any audit reports received to the sponsor.

11.2 Management of Protocol Amendments and Deviations

11.2.1 Modification of the Protocol

Any changes in the required procedures defined in this protocol, except those necessary to remove an apparent, immediate hazard to the participant, must be reviewed and approved by

the sponsor or designee. Amendments to the protocol (including emergency changes) must be submitted in writing to the investigator's IRB/IEC, along with any applicable changes to the ICF, for approval before participants can be enrolled into an amended protocol.

11.2.2 Protocol Deviations

A deviation from the protocol is an unintended or unanticipated departure from the procedures or processes approved by the sponsor and the IRB/IEC and agreed to by the investigator. A significant deviation occurs when there is nonadherence to the protocol or to local regulations or ICH GCP guidelines that may or may not result in a significant, additional risk to the participant or impacts the integrity of study data.

The investigator or designee must document and explain in the participant's source documentation any deviation from the approved protocol. The investigator may implement a deviation from, or a change of, the protocol to eliminate an immediate hazard/safety risk to study participants without prior IRB/IEC approval. As soon as possible after such an occurrence, the implemented deviation or change, the reasons for it, and any proposed protocol amendments should be submitted to the IRB/IEC for review and approval, to the sponsor for agreement, and to the regulatory authorities, where required.

In order to keep deviations from the protocol to a minimum, the investigator and relevant site personnel will be trained in all aspects of study conduct by the sponsor/sponsor representative. This training will occur either as part of the investigator meeting or site initiation. Ongoing training may also be performed throughout the study during routine site monitoring activities.

11.3 Study Termination

Although Evelo has every intention of completing the study, Evelo reserves the right to discontinue the study at any time for clinical or administrative reasons.

If the study is prematurely terminated or suspended, the sponsor or investigator shall promptly inform the investigators, the IECs/IRBs, the regulatory authorities, and any contract research organization(s) used in the study of the reason for termination or suspension, as specified by the applicable regulatory requirements. The investigator shall promptly inform the participant and should assure appropriate participant therapy and/or follow-up.

The EOS is defined as the date on which the last participant completes the last visit (includes follow-up visit).

11.3.1 Study Halting Criteria

The study will be halted if any of the following occur:

- One death considered definitely, probably, or possibly related to the study drug
- Two or more participants with an SAE considered definitely, probably, or possibly related to the study drug
- Three or more participants with grade 3 AEs of the same type considered definitely, probably, or possibly related to the study drug

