6.2.1.1.2 Serious Adverse Events

An SAE is defined as any event that

- results in death
- is immediately life threatening
- requires inpatient hospitalization or prolongation of existing hospitalization
- results in persistent or significant disability/incapacity
- is a congenital anomaly/birth defect

Important medical events that may not result in death, be life threatening, or require hospitalization may be considered SAEs when, based upon appropriate medical judgment, they may jeopardize the participant or may require medical or surgical intervention to prevent one of the outcomes listed in this definition. Examples of such medical events include allergic bronchospasm requiring intensive treatment in an emergency room or at home, blood dyscrasias or convulsions that do not result in inpatient hospitalization, or the development of drug dependency or drug abuse.

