6.2.1.2.1 Assessment of Severity

The severity, or intensity, of an AE refers to the extent to which an AE affects the participant's daily activities or their health. The intensity of the AE will be rated in accordance with the CTCAE version 5.0.

Changes in the severity of an AE should be documented to allow an assessment of the duration of the event at each level of intensity to be performed. Adverse events characterized as intermittent do not require documentation of onset and duration of each episode.

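### The third halting criterion counts only grade 3 events, so, as written, two grade 3 events plus one grade 4 SAE of the same type do not halt the study, although three grade 3 events would

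*Protocol*

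**What the plan says.** Protocol 11.3.1 is a mandatory list: "The study will be halted if any of the following occur". The first criterion is one related death. The second is "Two or more participants with an SAE considered definitely, probably, or possibly related to the study drug", with no restriction to one type of event. The third is "Three or more participants with grade 3 AEs of the same type considered definitely, probably, or possibly related to the study drug". In all three, related means definitely, probably or possibly related.

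Protocol 6.2.1.2.1 has intensity rated by CTCAE version 5.0 and adds that "Changes in the severity of an AE should be documented". Seriousness is a separate attribute, defined in 6.2.1.1.2. One of its conditions is that the event "is immediately life threatening".

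On oversight, 11.1.1 states: "There will be no safety review committee or data monitoring committee". Under 11.3 the sponsor "reserves the right to discontinue the study at any time for clinical or administrative reasons".

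**The concern.** A halting rule should never be easier on a worse set of events than on a milder one. The third criterion names a single grade and sets no floor, and nothing elsewhere in the protocol or SAP extends it upwards. A grade 4 event therefore adds nothing to the count of three. The SAE criterion does not make up for this when only one participant has an SAE.

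The list exists to commit the sponsor to a halt in advance. Where it fails to trigger, stopping rests on sponsor discretion, and no committee is in place to correct a literal reading. At stake is participant safety during the study. No estimand, analysis or sample size is affected.

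**Working it through.** The plan gives no figure to reproduce, so the check is a logical one.

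**Rule as written (11.3.1).** Halt if any of these holds:
- participants with a related death ≥ 1
- participants with a related SAE ≥ 2
- participants with a related AE of the same type and grade = 3: ≥ 3

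**The case in question.** Three participants, all events related, non-fatal and of the same type.

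| Cluster | Deaths (need 1) | SAE participants (need 2) | Grade 3 participants (need 3) | Halt? |
|---|---|---|---|---|
| Three grade 3, non-serious | 0 | 0 | 3 | Yes |
| Two grade 3 non-serious, one grade 4 serious | 0 | 1 | 2 | No |

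**All patterns, if every grade 4 event is serious.** Each participant is one of three kinds: grade 3 non-serious, grade 3 serious, grade 4 serious. The number of unordered groups of three is C(3+3−1, 3) = C(5, 3) = 10. To escape, a group needs at most one SAE and at most two grade 3 events. Only the second row of the table qualifies: 1 of 10.

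**How long the gap lasts under that assumption.** Add a fourth participant with a related event of that type. If it is grade 3, the grade 3 count becomes 2 + 1 = 3. If it is grade 4, and so serious, the SAE count becomes 1 + 1 = 2. Either way the study halts, so the delay is at most one participant. A further participant with a related SAE of any other type also triggers the halt, because the SAE criterion is not tied to type.

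**All patterns, if grade 4 events can be non-serious (assumption).** There are now four kinds, giving C(4+3−1, 3) = C(6, 3) = 20 groups. Write 3n and 3s for grade 3 non-serious and serious, and 4n and 4s for grade 4. The groups that do not halt are:
- 3n 3n 4n
- 3n 3n 4s
- 3n 3s 4n
- 3n 4n 4n
- 3n 4n 4s
- 3s 4n 4n
- 4n 4n 4n
- 4n 4n 4s

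That is 8 of 20. Each has at most one SAE and at least one grade 4 event.

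**With the third criterion read as grade ≥ 3.** Every group contains three participants at grade 3 or above, so all halt: 0 of 10 and 0 of 20 escape.

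**The case against.** The wording and the counts are not in dispute. The case on the other side is that the effect is small.

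- **The pattern is narrow.** If every grade 4 event is serious, it needs exactly one participant with a related SAE in the whole study and exactly two participants with non-serious related grade 3 events of the same type as that grade 4 SAE. The delay is then at most one participant. This stands. Phase 1 also reported no SAEs and no AEs of severe intensity (Protocol section 1), so such a cluster looks unlikely, although the documents give no rate.
- **Severity changes are documented.** An event that passed through grade 3 on its way to grade 4 has a recorded grade 3 stage and could be counted. This stands in part. The protocol states no such counting rule for halting, and an event first recorded at grade 4 has no grade 3 stage to count.
- **The figure of 8 of 20 rests on an assumption.** This also stands. Whether a grade 4 event can be non-serious is not settled by the documents, so the conclusion should rest on the single pattern.
- **Other safeguards exist.** SAEs are reported within 24 hours (6.2.1.3.1), the clinical safety team is unblinded for SUSAR handling (5.6.1), the sponsor reviews SUSARs against cumulative experience (6.2.1.3.2), and a participant with a serious or intolerable AE is discontinued where the investigator judges it necessary (4.2). These would probably bring the one SAE to notice quickly. None is a mandatory halt.
- **A threshold was probably intended.** SAP 10.2 writes grade 3 or above when it means one. That is a fair inference, and it makes this look like a drafting omission. It also means the correction should be uncontroversial.

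**Conclusion.** The concern holds. As written, 11.3.1 halts on three non-serious grade 3 events but not when one of them is instead a grade 4 SAE. Its size is one escaping pattern of 10, with a delay of at most one participant, if every grade 4 event is serious. It is 8 of 20 if grade 4 events can be non-serious; in that case three non-serious grade 4 events would not halt the study.

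Both counts assume related, non-fatal, same-type events in three different participants and a literal reading of the criterion. If events that passed through grade 3 are counted, the gap is limited to events first recorded at grade 4. Nothing here measures how likely such clusters are. The change should be made, because a stated safety rule gives the wrong ordering and the correction is simple, but the practical effect is probably small.

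**What to change.** Reword the third criterion so that it counts three or more participants with related AEs of grade 3 or above of the same type. The participant count, the relatedness test and the resulting action stay as the sponsor set them.

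The cost is a protocol amendment. Under 11.2.1, "Amendments to the protocol (including emergency changes) must be submitted in writing to the investigator's IRB/IEC" for approval, and this change can be bundled with the next one. The downside is a slightly higher chance of a halt, and only in clusters worse than one that already halts the study.

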13.1 Appendix: Contraceptive Guidance and Collection of Pregnancy Information

Definitions:

Women of Child-Bearing Potential

A woman is considered fertile following menarche and until becoming postmenopausal unless permanently sterile (see below).

Women in the following categories are not considered WOCBP:

1. Premenarchal
2. Premenopausal female with 1 of the following:
 - Documented hysterectomy
 - Documented bilateral salpingectomy
 - Documented bilateral oophorectomy
3. Postmenopausal female
 - A postmenopausal state is defined as no menses for 12 months without an alternative medical cause. A high FSH level in the postmenopausal range must be used to confirm a postmenopausal state in women not using hormonal contraception or HRT. However, in the absence of 12 months of amenorrhea, an FSH measurement is insufficient.
 - Females on HRT and whose menopausal status is in doubt will be required to use one of the non-oestrogen hormonal highly effective contraception methods if they wish to continue their HRT during the study.

Contraception Guidance:**Male participants**

Male participants must participate according to one of the following criteria:

- Be abstinent from penile-vaginal intercourse as their usual and preferred lifestyle (abstinent on a long term and persistent basis) and agree to remain abstinent.
- Use a male condom during each episode of penile penetration during their participation in the study and for 90 days after the last dose of study drug. In addition, male participants must refrain from donating sperm for the duration of the study and for at least 90 days following their final visit.
- Have had a vasectomy, and the absence of sperm has been confirmed in the ejaculate.

Female participants

Female participants of child-bearing potential are eligible to participate if they agree to use a highly effective contraceptive method consistently and correctly as described in Table 13-1.

Table 13-1 Highly Effective Contraceptive Methods

Highly Effective Contraceptive Methods That Are User Dependent^a
Failure rate of <1% per year when used consistently and correctly.
Combined (estrogen and progestogen containing) hormonal contraception associated with inhibition of ovulation ^b 
• Oral• Intravaginal• Transdermal
Progestogen only hormonal contraception associated with inhibition of ovulation ^b 
• Oral• Injectable
Highly Effective Methods That Are User Independent^a

• Implantable progestogen only hormonal contraception associated with inhibition of ovulation^b• Intrauterine device (IUD)• Intrauterine hormone-releasing system (IUS)• Bilateral tubal sterilization

Vasectomized partner A vasectomized partner is a highly effective contraception method provided that the partner is the sole male sexual partner of the WOCBP and the absence of sperm has been confirmed. If not, an additional highly effective method of contraception should be used.
Sexual abstinence Sexual abstinence is considered a highly effective method only if defined as refraining from heterosexual intercourse during the entire period of risk associated with the study drug. The reliability of sexual abstinence needs to be evaluated in relation to the duration of the study and the preferred and usual lifestyle of the participant.
Table Notes: a) Typical use failure rates may differ from those when used consistently and correctly. Use should be consistent with local regulations regarding the use of contraceptive methods for participants participating in clinical studies. b) Hormonal contraception may be susceptible to interaction with the study drug, which may reduce the efficacy of the contraceptive method. In this case, a highly effective method of contraception plus condoms should be used during their participation in the study up to and including at least 1 complete menstrual cycle (≥ 28 days) for women and 90 days for men post last dose.

Pregnancy Testing:

- A WOCBP should only be included after a negative serum HCG pregnancy test.
- Pregnancy testing is required at screening, randomization, and 14 days after the last dose at the follow-up visit.
- Pregnancy testing will be performed whenever a menstrual cycle is missed or when pregnancy is otherwise suspected.

Collection of Pregnancy Information:

For male participants with partners who become pregnant:

- The investigator will attempt to collect pregnancy information on any male participant's female partner who becomes pregnant while the male participant is in this study. This applies to all male participants who receive EDP1815.
- After obtaining the necessary signed informed consent from the pregnant female partner directly, the investigator will record pregnancy information on the appropriate form and submit it to the sponsor within 24 hours of learning of the partner's pregnancy. The female partner will also be followed to determine the outcome of the

pregnancy. Information on the status of the mother and child will be forwarded to the sponsor. Generally, the follow-up will be no longer than 8 weeks following the estimated delivery date. Any termination of the pregnancy will be reported regardless of fetal status (presence or absence of anomalies) or indication for the procedure.

For female participants who become pregnant:

- The investigator will collect pregnancy information on any female participant who becomes pregnant while participating in this study. Information will be recorded on the appropriate form and submitted to the sponsor within 24 hours of learning of a participant's pregnancy. The participant will be followed to determine the outcome of the pregnancy. The investigator will collect follow-up information on the participant and the neonate and the information will be forwarded to the sponsor. Generally, follow-up will not be required for longer than 6 to 8 weeks beyond the estimated delivery date. Any termination of pregnancy will be reported, regardless of fetal status (presence or absence of anomalies) or indication for the procedure.
- While pregnancy itself is not considered to be an AE or SAE, any pregnancy complication or elective termination of a pregnancy will be reported as an AE or SAE. A spontaneous abortion is always considered to be an SAE and will be reported as such. Any post-study pregnancy-related SAE considered reasonably related to the study drug by the investigator will be reported to the sponsor as described in Section 6.2.1.3.1. While the investigator is not obligated to actively seek this information in former study participants, he or she may learn of an SAE through spontaneous reporting.
- Any female participant who becomes pregnant while participating in the study will discontinue study drug.

